A phase 3, long-term extension study (SM04690-OA-05) is also being performed to monitor the long-term safety, tolerability, and efficacy of treatment of SM04690 or placebo previously injected in the target knee joints of subjects with moderately to severely symptomatic OA from a Samumed-sponsored SM04690-OA phase 2 or phase 3 study. This study is a multicenter, observational study in subjects that have previously been treated with SM04690 or placebo injected into the target knee joint. Approximately 2000 subjects will be consented and will participate in a 60 month follow-up period. Clinic visits are scheduled at Months 6, 12, 24, 36, 48, and 60 [End of study (EOS)]/Early Termination (ET).

This phase 2 study, SM04690-OA-04, is a placebo-controlled, double-blind, parallel group study of four concentrations of SM04690 (0.03, 0.07, 0.15, and 0.23 mg per 2 mL injection) injected into the target knee joint of subjects with moderately to severely symptomatic OA. Based upon the interim data analysis of SM04690-OA-02, key phenotypes of laterality (unilateral vs bilateral) as well as chronic pain (as measured by the Widespread Pain Index) were identified as confounding variables impacting the overall assessment of both radiologic and clinical efficacy outcomes. The design of SM04690-OA-04 is based upon the SM04690-OA-02 design while assessing strategies to combat the confounding impact of laterality and chronic pain.

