5.1 PARTICIPANT INCLUSION CRITERIA

In order to be eligible for the study, subjects must fulfill all of the following criteria:

1. Males and females between 40 and 80 years of age, inclusive, in general good health
2. Ambulatory
3. Diagnosis of femorotibial OA in the target knee by standard American College of Rheumatology (ACR) criteria at Screening Visit 1 (clinical AND radiographic criteria); OA of the knee is not to be secondary to any rheumatologic conditions (e.g., rheumatoid arthritis)
4. Pain compatible with OA of the knee(s) for at least 26 weeks prior to Screening Visit 1
5. Primary source of pain throughout the body is due to OA in the target knee
6. Daily OA knee pain diary average NRS intensity score ≥ 4 and ≤ 8 in the target knee on the 11-point (0-10) NRS scale for the 7 days immediately preceding Day 1
7. Pain NRS scores recorded for the target knee on at least 4 out of the 7 days immediately preceding Day 1
8. Daily OA knee pain diary average NRS intensity score < 4 in the non-target knee on the 11-point (0-10) NRS scale for the 7 days immediately preceding Day 1
9. Pain NRS scores recorded for the non-target knee on at least 4 out of the 7 days immediately preceding Day 1
10. Total WOMAC score of 96-192 (out of 240) for the target knee at baseline regardless of if the subject is on symptomatic oral treatment (baseline questionnaire completed during the screening period prior to randomization)
11. Willingness to use an electronic diary on a daily basis in the evening for the screening period and 24-week study duration
12. Negative drug test for opioids and drugs of abuse, except alcohol and marijuana, at Screening Visit 1
13. Subjects with depression or anxiety must be clinically stable for 12 weeks prior to Screening Visit 1 and, if on treatment for depression or anxiety, be on 12 weeks of stable therapy
14. Full understanding of the requirements of the study and willingness to comply with all study visits and assessments
15. Subjects must have read and understood the informed consent form, and must have signed it prior to any study-related procedure being performed
16. Subject's Screening Visit 1 visit must occur while enrollment into the randomization cohort for which they are eligible is open

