
A general physical examination will be conducted at Screening Visit 1, Day 1, and Weeks 4, 12, and 24 (EOS)/ET. Results of the physical examination will be noted in the source documents. Any clinically significant finding noted prior to study medication injection should be recorded as medical history. If it is found after study medication injection, it should be reported as a TEAE.

Knee Examination

A knee examination of both knees will be conducted at Screening Visit 1, Day 1, and Weeks 4, 12, and 24 (EOS)/ET. Results of the knee examination will be noted in the source documents. Any clinically significant finding noted prior to study medication injection should be recorded as medical history. If it is found after study medication injection, it should be reported as a TEAE.

Presence of bilateral knee OA (yes/no) will be recorded in the eCRF at Screening Visit 1. If the subject has OA in both knees, the site is to establish the target knee as the knee with greater pain at Screening Visit 1 based on the subject's evaluation and the Investigator's clinical judgment.

Misalignment of both knees will be assessed by the Investigator during the knee examination at Screening Visit 1. In the opinion of the Investigator, subjects with significant and clinically evident misalignment in either knee that would impact subject function must be excluded from the study.

Vital Signs

Vital signs will be measured by a qualified staff member at Screening Visit 1, Day 1, and Weeks 4, 12, and 24 (EOS)/ET.

At each time point, the following vital signs will be measured:

- Body temperature
- Pulse rate
- Respiration rate
- Blood pressure (systolic and diastolic) after the subject rests (sitting or supine) for at least 5 minutes; same resting position should be used for all blood pressure

measurements throughout the study

Any measurement that is, in the opinion of the Investigator, abnormal AND clinically significant must be recorded as medical history if found prior to study medication injection or as a TEAE if found after study medication injection.

Height and Weight

Height measurements will be taken at Screening Visit 1 only. Weight measurements will be taken at Screening Visit 1 and Week 24 (EOS)/ET.

Radiograph of Knee Joints

Radiograph of the knee joints will be taken at Screening Visit 1 and Week 24 (EOS)/ET.

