Detailed instructions for obtaining and managing the radiographs will be provided to the investigational center prior to the initiation of subject enrollment. The intent (as described in the Image Review Charter – Image Acquisition Guidelines) is that radiographs should be obtained in the posterior-anterior (PA) view, whenever possible.

All radiographs will be submitted to an independent radiologist who will document disease stage according to the Kellgren-Lawrence grading scale for compliance with inclusion/exclusion criteria, as well as JSW for efficacy assessments.

Widespread Pain Index and Symptom Severity (WPI&SS) Form

The WPI&SS assessment consists of a body map that determines a subject's areas of pain or tenderness [Widespread Pain Index (WPI)] and symptom severity (SS) questions ([Clauw 2014](#)). A WPI&SS assessment will be completed by the subject at Screening Visit 1 on paper.

Upon completion of the WPI&SS assessment, the subject will sign/initial and date the source document to indicate that the assessments are reported accurately.

The WPI&SS assessment sheets will be provided by the Sponsor and may not be reproduced.

Electronic Diary Device Provision and Training

Electronic diary device provision will occur at Screening Visit 2. Subjects will be trained on electronic diary and questionnaire completion at Screening Visit 2. Subject training will include details on what medications are NSAIDs. Detailed instructions for subject training and electronic questionnaire completion will be provided to the investigational center. Electronic devices are to be returned to the site at Week 24 (EOS)/ET.

Electronic devices will store completed questionnaire data for up to 30 days. Therefore, it is recommended that site personnel review study subject ePRO data and compliance reports in the ePRO vendor web portal (StudyWorks) at least once a week or more frequently as needed to ensure timely subject completion and transmission of questionnaire data between study visits.

Pain Numeric Rating Scale (NRS)

The pain NRS is an 11-point scale (0-10) for subject self-reporting of average knee pain in the last 24 hours. A pain NRS for each knee will be completed daily by the subject during the screening period from Screening Visit 2 until Day 1 to assess subject ability to be compliant with a daily pain assessment. During the screening period, daily pain NRS assessments will be

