completed by subjects in the evening (between 5:00 pm and 11:59 pm) remotely on their electronic devices for each knee to collect average knee pain in the last 24 hours. Subject electronic diary compliance for daily pain NRS over the screening period will be reviewed at Day 1 prior to randomization. After screening, starting on Day 1, daily pain NRS assessments are to be completed by subjects in the evening (between 5:00 pm and 11:59 pm) remotely on their electronic devices for the target knee only. Refer to [Section 7.3.7](#) for a schedule of electronic diary and questionnaire completion.

Subjects will complete the pain NRS on the Sponsor-provided electronic device. Subjects will receive notifications reminding them to complete the daily pain NRS assessment. If a subject does not complete the electronic diary for pain NRS for at least 4 out of 7 days in a given week, this will be considered a protocol deviation due to subject non-compliance, but the subject should not be removed from the study unless the Investigator determines it is in the best interest of the subject.

Increases in pain should only be considered TEAEs if reported by the subject, regardless of pain NRS scores.

Nonsteroidal Anti-Inflammatory Drugs (NSAIDs) Electronic Diary

The daily electronic diary of NSAID usage will document subject usage of any NSAID medication as “yes” or “no” in response to the following question, “Did you take any medication that is an NSAID in the last 24 hours?”. Starting on the day of Screening Visit 2 after the site visit, daily electronic diary of NSAID usage is to be completed by subjects in the evening (between 5:00 pm and 11:59 pm) remotely on their electronic devices. Refer to [Section 7.3.7](#) for a schedule of electronic diary and questionnaire completion.

Subjects will complete electronic diary of NSAID usage on the Sponsor-provided electronic device. Subjects will receive notifications reminding them to complete the electronic diary of NSAID usage. If a subject does not complete the electronic diary of NSAID usage for at least 4 out of 7 days in a given week, this will be considered a protocol deviation due to subject non-compliance, but the subject should not be removed from the study unless the Investigator determines it is in the best interest of the subject.

Western Ontario and McMaster Universities Arthritis Index (WOMAC)

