5.2.1. Pain Numeric Rating Scale

The Pain NRS is an 11-point scale (0-10) for subject self-reporting of average knee pain in the last 24 hours, where 0 represents no pain and 10 represents extreme pain. Subjects were prompted to report average pain in the target knee daily on their electronic device (between 5:00 pm and 11:59 pm) from Screening Visit 2 through the end of the study. An average weekly score (referred to as weekly Pain NRS) was calculated for each subject if they had provided a response for at least 4 out of 7 days in a given week. Weeks are defined as Day -7 through Day -1 (day before treatment) for baseline, Day 1 (day of treatment) through Day 7 for Week 1, Day 8 through Day 14 for Week 2, and so on.

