7.2. ANCOVA Model for Continuous Efficacy Outcomes

ANCOVA models will be used for all continuous efficacy outcome measures summarized by change from baseline in order to test the following four hypotheses:

$$H_0: (\beta_i - \beta_0) = 0$$

$$H_A: (\beta_i - \beta_0) \neq 0, \text{ where } i = 1,2,3,4$$

In the statement above, β is the least squares estimate in the change in the continuous efficacy outcome from baseline at each timepoint (where β_0 is the estimate for vehicle), and i represents each of the four SM04690 treatment groups.

Least squares estimate of difference between each treatment group and placebo in the change in the continuous efficacy outcome from baseline at each timepoint, adjusted for baseline value, will be reported along with unadjusted 95% confidence intervals and P values.

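### Pain in the non-target knee is recorded in both-knee diaries before injection but used only for eligibility; adding its baseline mean as a covariate costs almost nothing and may modestly improve precision

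*SAP*

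**What the plan says.** **Collection.** Protocol 7.1.1 (Pain NRS) states: "A pain NRS for each knee will be completed daily by the subject during the screening period from Screening Visit 2 until Day 1". From Day 1 the diary is completed "remotely on their electronic devices for the target knee only". Non-target pain therefore exists only as a baseline measurement.

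**Use.** Protocol 5.1 has two criteria on it. Criterion 8 requires "Daily OA knee pain diary average NRS intensity score < 4 in the non-target knee" over the 7 days before Day 1, and criterion 9 requires "Pain NRS scores recorded for the non-target knee on at least 4 out of the 7 days immediately preceding Day 1". Diary compliance is reviewed on Day 1 before randomisation. I found no other use. SAP 5.2.1 describes the scale for one knee only ("Subjects were prompted to report average pain in the target knee daily on their electronic device"), and SAP 10.2 does not list non-target pain among the baseline characteristics.

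**Models.** SAP 7.2 reports least squares differences "adjusted for baseline value, will be reported along with unadjusted 95% confidence intervals and P values". The MMRM in 7.5.2 has treatment, week, their interaction and the baseline value. The vehicle-sham ANCOVA in 7.5.4 adjusts for baseline value. Protocol 10.4.2, 10.4.3 and 10.4.7 specify the same adjustment.

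**Laterality.** Protocol 2.2 says that laterality and chronic pain, seen in the interim data of the earlier phase 2 trial, "were identified as confounding variables impacting the overall assessment of both radiologic and clinical efficacy outcomes". Laterality enters this trial as a binary code: "Presence of bilateral knee OA (yes/no) will be recorded in the eCRF at Screening Visit 1". It is a randomisation stratum (protocol 10.6.1, SAP 3.2), defines two of the three analysis populations (SAP 7.1), and appears in four of the six additional subgroups (SAP 7.5.5). It is not a covariate in the all-subjects ANCOVA.

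**The concern.** The sponsor attributes part of the difficulty in the earlier trial to laterality, and this trial records how much the other knee hurts on a numeric scale before injection. The analysis then carries forward only the yes/no code. Within either category, criterion 8 lets the non-target weekly mean lie anywhere from 0 to just under 4. In the two unilateral populations the code is constant and can explain no variance, whereas a continuous score still could.

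Pain in the other knee could plausibly affect WOMAC function, patient global assessment and target-knee pain ratings. If it predicts Week 24 change beyond the outcome's own baseline, leaving it out puts explainable variation in the error term and makes the intervals wider than necessary. This matters most in the unilateral population without widespread pain, whose cohort is capped at 240 (protocol 7.3.2), about 40 per arm.

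**Working it through.** **The plan's own figure.** About 630 subjects in six equal arms gives 630/6 = 105 per arm. The documents give no power, effect size or SD, so 630 cannot be re-derived. As a reference, at two-sided 5% and 80% power, 105 per arm detects (1.960 + 0.842) × √(2/105) = 0.387 SD.

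**Inputs from the documents**
- Primary contrasts: four doses against vehicle (SAP 7.2), so 5 × 105 = 525 subjects. Sham is not part of them.
- Smallest main population: 240/6 = 40 per arm, so 5 × 40 = 200 subjects in active and vehicle arms.
- Range of the covariate: 0 to under 4 (criterion 8).

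**Input assumed.** r is the partial correlation of baseline non-target NRS with Week 24 change, given the other terms in the model. The documents give no value; 0.1 to 0.3 is used.

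**Gain.** The SE is multiplied by √(1 − r²). The equivalent number of extra subjects is N × (1/(1 − r²) − 1).

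| r | SE reduction | Extra subjects, N = 525 | Extra subjects, N = 200 |
|---|---|---|---|
| 0.1 | 1 − √0.99 = 0.5% | 525 × 0.0101 = 5 | 2 |
| 0.2 | 1 − √0.96 = 2.0% | 525 × 0.0417 = 22 | 8 |
| 0.3 | 1 − √0.91 = 4.6% | 525 × 0.0989 = 52 | 20 |

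At the difference that has 80% power without the covariate, 105 per arm, power becomes 80.3%, 81.5% and 83.5%, after allowing for the lost degree of freedom.

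**Cost if the covariate is useless (r = 0).** Expected variance is multiplied by 1 + 1/(df − 1), with df the error degrees of freedom after adding it to a five-arm model (five arm means, own baseline, new covariate).
- 105 per arm: df = 525 − 7 = 518; 1 + 1/517 = 1.0019; intervals 0.1% wider.
- 40 per arm: df = 200 − 7 = 193; 1 + 1/192 = 1.0052; intervals 0.26% wider.

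Break-even |r| is √(1 − 1/1.0019) ≈ 0.04 and √(1 − 1/1.0052) ≈ 0.07. If each dose is instead fitted against vehicle alone, the variance factors are 1.0049 and 1.0133 and the break-even values 0.07 and 0.115.

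**Simulation check** (five arms, 4000 replicates). The ratio of SE with to SE without the covariate was 1.001, 0.981 and 0.955 at r = 0, 0.2 and 0.3 with 105 per arm, and 1.003, 0.983 and 0.956 with 40 per arm. This agrees with the formulas.

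**Effect of the entry cap.** Restricting the covariate to below 4 reduces its correlation. With R the unrestricted correlation and u the ratio of restricted to unrestricted SD, r = R·u/√(1 − R² + R²u²). Four assumed distributions were tried (normal with mean 1 to 4 and SD 2 to 2.5, clipped to 0-10). R = 0.2 became about 0.11 to 0.16, and R = 0.3 became about 0.17 to 0.24. Across r = 0.11 to 0.24 the SE reduction is about 0.6 to 3%.

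**The case against.** The strongest reply is that nothing in the plan is wrong. With randomisation stratified by laterality and WPI/SSQ2, an ANCOVA on own baseline gives a valid contrast, and protocol and SAP agree with each other. Laterality is handled by stratification, populations and subgroups, and criterion 8 limits contralateral pain by design. The protocol tests no formal hypotheses (10.2), and a change of a few percent in SE is not shown to alter dose selection. All of this stands, and it limits the point to an optional improvement.

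A reader might infer three stronger claims that the documents do not support:
- **That outcomes are confounded between arms by contralateral pain.** Protocol 2.2 does use the word confounding, but about the earlier trial's phenotypes. Under randomisation, omitting a baseline predictor costs precision and does not bias the contrast.
- **That non-target NRS is a known predictor.** Protocol 2.2 names laterality and widespread pain, not pain intensity in the other knee. No document gives a correlation, or the distribution of the score within strata.
- **That every interval is wider than necessary.** Below the break-even correlation the covariate slightly widens intervals, and nothing suggests a gain for medial JSW.

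It is also fair that the phenotypes the protocol actually names, laterality and WPI/SSQ2, are missing from the all-subjects ANCOVA. That is the more direct omission, and non-target pain should supplement those factors rather than replace them. What the objections do not show is a material downside, or that the covariate is redundant where laterality is constant.

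**Conclusion.** The point holds as a minor, nearly free improvement in precision. A pre-randomisation measurement that entry requires is left out of every model. Using it would reduce the SE by about 0.5 to 4.6% if the partial correlation is 0.1 to 0.3, with the lower part more likely because of the cap below 4. If the correlation is zero, the loss is about 0.1% of interval width at 105 per arm and 0.3% at 40 per arm in a five-arm model. The size rests wholly on the assumed correlation. The near-absence of cost follows from the design, provided the few missing values are handled by rule.

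**What to change.** Before unblinding:
- In SAP 7.2, 7.5.2 and 7.5.4, and so in the estimates passed to MCP-Mod in 7.6, add the mean non-target NRS over Day -7 to Day -1 as a covariate for Pain NRS, WOMAC, PTGA, KOOS and KOOS-PS wherever those sections analyse them. Leave it out for mJSW.
- In the all-subjects model, also include the stratification factors laterality and WPI/SSQ2.
- State a simple rule for FAS subjects without a value. Criterion 9 covers eligible subjects, but the FAS includes anyone randomised and injected, so eligibility deviations could leave a few gaps.
- List the variable in SAP 10.2, and align protocol 10.4.2, 10.4.3 and 10.4.7, which now specify adjustment for baseline value only.

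The cost is one degree of freedom for the covariate, one for each binary stratification factor in the all-subjects model, and matching text edits in the two documents. No new data are needed.

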7.3. Analysis of Primary Efficacy Endpoints

The change from baseline in weekly Pain NRS, WOMAC Pain, WOMAC Function and mJSW at Week 24 will be analyzed with the ANCOVA model described in Section 7.2. Figures displaying the change in outcome over time will be provided for the FAS and mFAS.

7.4. Analysis of Secondary Efficacy Endpoints

The change from baseline in PTGA at Week 24 will be analyzed with the ANCOVA model described in Section 7.2. Figures displaying the change in PTGA over time will be provided for the FAS and mFAS.

7.5. Analysis of Exploratory Efficacy Endpoints

7.5.1. Additional Timepoints and Outcome Measures

The change from baseline in the parameters described below will be analyzed with the ANCOVA model described in Section 7.2.

1. WOMAC Pain at Weeks 4, 8, 12, 16, and 20
2. WOMAC Function at Weeks 4, 8, 12, 16, and 20
3. WOMAC Total at Weeks 4, 8, 12, 16, 20, and 24
4. Weekly Average of Pain NRS at all weeks, except Week 24
5. PTGA at Weeks 4, 8, 12, 16, and 20
6. KOOS at Weeks 4, 8, 12, 16, 20, and 24
7. KOOS-PS at all weeks
8. PGA at Weeks 4, 12, and 24

7.5.2. Mixed-Effects Model for Repeated Measures

Change over time in primary and secondary endpoints (weekly Pain NRS, WOMAC Pain, WOMAC Function and PTGA) as well as weekly measures (KOOS-PS and NSAID usage) will be characterized using mixed-effects models for repeated measures (MMRM). The models will estimate change from baseline with treatment, week, treatment×week interaction and baseline value as covariates.

For weekly measured outcomes, MMRM will be estimated assuming a Toeplitz variance-covariance matrix. The Toeplitz structure is a more generalized form of autogressive-1 (AR1) structure, allowing the data to inform how the correlation between within-subject observations decreases over time instead of implicitly defining a uniform decay structure. For monthly measured outcomes, MMRM will be estimated assuming an unstructured variance-covariance matrix, allowing the data to fully inform the correlation between within-subject observations. (Kincaid 2005)

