9.4. Handling of Missing Data

Missing data will not be imputed for the efficacy analyses described in Section 7. A sensitivity analysis will be performed using the last observation carried forward (LOCF) approach to impute missing assessments at Week 24 for weekly Pain NRS, WOMAC Pain, WOMAC Function and PTGA. This will then be followed by the ANCOVA analysis described in Section 7.2. Since single imputation is not necessary for the PPAS with complete data, LOCF analysis will be performed on the FAS and mFAS, and repeated for the OA phenotypes described in Section 7.1.

In addition, a second sensitivity analysis for change from baseline in weekly Pain NRS, WOMAC Pain, WOMAC Function and PTGA will be conducted using MMRM as outlined in Section 7.5.2.

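### The MMRM used as a missing-data check has no baseline-by-week term, so its Week 24 estimate departs slightly from the ANCOVA even when nothing is missing

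*SAP*

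**What the plan says.** SAP 7.5.2 lists the fixed effects of the repeated-measures model: "The models will estimate change from baseline with treatment, week, treatment×week interaction and baseline value as covariates". Treatment is allowed to act differently by week. Baseline is not, and no other section of either document adds that interaction.

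The same section sets the covariance. For WOMAC and PTGA: "For monthly measured outcomes, MMRM will be estimated assuming an unstructured variance-covariance matrix". For Pain NRS, KOOS-PS and NSAID use: "For weekly measured outcomes, MMRM will be estimated assuming a Toeplitz variance-covariance matrix".

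The main analysis is an ANCOVA. SAP 7.2 reports the treatment difference "in the change in the continuous efficacy outcome from baseline at each timepoint, adjusted for baseline value", and SAP 7.3 says that change in the four primary outcomes "at Week 24 will be analyzed with the ANCOVA model described in Section 7.2". Because the ANCOVA is fitted timepoint by timepoint, Week 24 has its own baseline slope.

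On missing data, SAP 9.4 states: "Missing data will not be imputed for the efficacy analyses described in Section 7". It then plans an LOCF analysis and "a second sensitivity analysis for change from baseline in weekly Pain NRS, WOMAC Pain, WOMAC Function and PTGA will be conducted using MMRM". mJSW has no MMRM, so the point concerns three of the four primary outcomes plus PTGA.

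**The concern.** The main analysis uses observed cases only. A reader who sees the ANCOVA and MMRM results side by side will put any difference down to missing data, because SAP 9.4 introduces the MMRM for that purpose. As specified, the two models also adjust for baseline differently, and that difference is present with no missing values at all. Part of the gap could be misread as sensitivity to dropout, or could mask it. If the slope of change on baseline differs across weeks, a common slope also costs a little precision at Week 24.

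**Working it through.** The plan states no figure to reproduce. The check is algebra, followed by simulation under stated assumptions.

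**Inputs from the documents.** About 630 subjects in six equal arms (Protocol 10.5, SAP 3.1), so 630/6 = 105 per arm. The unilateral cohort without widespread pain is capped at 240 (Protocol 7.3.2), so 240/6 = 40 per arm. There are six monthly assessments (Weeks 4 to 24) and 24 weekly ones. No SD, correlation or effect size is given.

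**Step 1: the gap.** Let D24 be the raw Week 24 difference in mean change between two arms and d0 their baseline mean difference. With complete data and the same arms in both models:
- ANCOVA: D24 − b24·d0
- MMRM as written: D24 − b_common·d0
- MMRM minus ANCOVA: (b24 − b_common)·d0

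Here b_common is a weighted average of the weekly slopes, with weights proportional to Σ⁻¹1. The gap is zero only if b24 = b_common or the arms have equal baseline means. With baseline×week added, every week has the same regressors, generalized least squares reduces to a separate regression per week, and the point estimates coincide under any covariance structure.

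**Step 2: its scale.** Under randomization d0 has mean zero and SD σ0·√(2/n). At n = 105, √(2/105) = 0.138, so the SD of the gap is about |b24 − b_common| × σ0 × 0.138.

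**Step 3: unstructured monthly models, complete data, 105 per arm.** Two sets of assumed values were simulated. Set A has baseline SD 1 and residual SD rising from 1.6 to 2.2. Set B is on the 0–100 scale, with baseline SD 14, follow-up SD 18 to 22 and residual correlation 0.85 per visit step.

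| Assumed drift | SD of gap | ANCOVA SE | Ratio | SE increase |
|---|---|---|---|---|
| A: slope constant at −0.4 | 0.0099 | 0.3028 | 0.03 | none |
| A: −0.3 to −0.5 | 0.0269 | 0.3028 | 0.09 | 0.3% |
| A: −0.2 to −0.6 | 0.0526 | 0.3028 | 0.17 | 1.4% |
| B: mild | 0.13 | about 2.8 | 0.05 | 0.1% |
| B: moderate | 0.43 | about 2.8 | 0.15 | 1.3% |
| B: strong | 0.87 | about 2.9 | 0.30 | 4.5% |

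The mean gap in set A was never more than 0.005 in size at 105 per arm. In set B the gap exceeded a quarter of a standard error in 41% of trials with strong drift, 10% with moderate drift and none with mild drift. The formula agrees. In B moderate the common slope was −0.21 against −0.45 at Week 24, and 0.24 × 14 × 0.138 = 0.46, against 0.43 simulated.

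At 40 per arm the gap is larger in points (B: 0.25, 0.65 and 1.39), but so is the standard error. In set A the ratios are 0.0231/0.490 = 0.05, 0.0410/0.490 = 0.08 and 0.0777/0.490 = 0.16.

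**Step 4: weekly Toeplitz models.** A Toeplitz matrix is symmetric about its centre, so the weights Σ⁻¹1 are too, and under linear drift b_common is the mid-study slope. For drift of −0.2 to −0.6 the formula gives 0.2 × 0.138 = 0.028. For −0.3 to −0.5 it gives 0.1 × 0.138 = 0.014. Eight simulated trials per setting gave SDs of 0.021 and 0.010 against an ANCOVA SE of 0.302.

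**Step 5: after adding baseline×week.** The largest difference in point estimates was about 6e-14 (unstructured) and 5e-13 (Toeplitz). The unstructured SE matched the ANCOVA (0.3028 in both). The Toeplitz SE did not: 0.265 against 0.302. Toeplitz imposes one variance on all weeks. With the SD rising linearly from 1.6 to 2.2 the average variance is (1.6² + 1.6 × 2.2 + 2.2²)/3 = 3.64, an SD of 1.91, and 1.91 × 0.138 = 0.264. The Week 24 SD alone gives 2.2 × 0.138 = 0.304.

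**The case against.** A common baseline slope is a legitimate, more parsimonious model. SAP 7.5.2 places the MMRM among the exploratory analyses, and SAP 9.4 nowhere says that it must reproduce the ANCOVA. The planned LOCF analysis reuses the ANCOVA, so one check already holds the model fixed while the handling of missing data changes. Protocol 10.2 says that no formal hypotheses are tested. All of this stands and limits the priority. It does not remove the reason to avoid an unneeded second difference between the main analysis and its check.

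A reader might also infer more than the documents support:

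- **That the slope must drift because correlation with baseline fades.** The slope of change on baseline is ρ·SD_t/SD_0 − 1, so a rising SD can offset a falling ρ. In set A with the slope constant at −0.4, the correlation falls from 0.6/√(0.36 + 2.56) = 0.35 to 0.6/√(0.36 + 4.84) = 0.26 with no drift at all. Entry limits on pain NRS and WOMAC total (Protocol 5.1) make a rise in SD after baseline plausible.
- **That the common slope reflects the early weeks.** This happened in the simulated unstructured monthly models, but under Toeplitz with linear drift it is the mid-study slope.
- **That Week 24 is biased.** A simulated shift of −0.3 to −1.1 points, with a standard error of 3.0 to 3.5, needed about 17% dropout tied to baseline in opposite directions by arm. Nothing in the documents points to that pattern.
- **That NSAID use is modelled only by the MMRM.** SAP 7.5.1 omits it from the ANCOVA list, but Protocol 10.4.7 applies ANCOVA to exploratory outcomes, so this is open to dispute.

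**Conclusion.** The point holds as a modest flaw in specification. The missing interaction is plain in SAP 7.5.2, and the complete-data gap of (b24 − b_common) times the baseline mean difference is exact. Its size rests on assumed slope drift, SDs and correlations. Within the ranges tried, the gap has mean near zero and an SD of roughly 0.05 to 0.3 standard errors, with the Week 24 standard error at most a few percent larger. With no true drift it is smaller still. It makes an ANCOVA–MMRM difference harder to interpret and does not threaten the trial's conclusions. Priority lies between an optional refinement and a recommended change, and the low cost favours making it.

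**What to change.** In SAP 7.5.2, add baseline×week to the fixed effects of every MMRM, monthly and weekly. State which arms enter the ANCOVA and the MMRM, and use the same arms in both. The SAP does not say whether sham subjects stay in either fit, and exact agreement depends on it.

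For weekly Pain NRS, also allow week-specific variances, for example through a heterogeneous Toeplitz structure. Otherwise the standard errors will still differ from the ANCOVA for a reason unrelated to missing data, and the SAP should not claim that the models differ only in how missing data are handled.

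The interaction costs 5 extra parameters in the monthly models (6 slopes instead of 1) and 23 in the weekly ones (24 instead of 1), which is small for about 630 subjects. Heterogeneous variances would add 23 more in the weekly models (24 variances instead of 1). No data collection changes.
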